6.4 Cumulative Radiation Dosimetry for [¹⁸F]Flutemetamol and [¹⁸F]FDG PET/CT Studies

The cumulative radiation dose to a patient participating in this clinical trial has been compiled from the dosimetry estimates for [¹⁸F]Flutemetamol (Section 6.1), [¹⁸F]FDG (Section 6.2), and the 2 head CT scans that will be performed as part of the PET/CT procedures. The greatest cumulative organ absorbed doses for the study are the bladder (74.9 mGy) and the gallbladder (57.9 mGy), while the effective dose is 13.2 mSv (Table 3).

Table 3. Radiation Dosimetry for [¹⁸F]Flutemetamol and [¹⁸F]FDG PET/CT Studies

Organ	FDG PET/CT Study		Flutemetamol PET/CT Study		Cumulative Organ Dose (mGy)
	FDG dose @ 10 mCi	Low Dose Head CT	Flutemetamol dose @ 5 mCi	Low Dose Head CT	
Adrenals	4.44	0.00048		2.41	0.00048
Bladder	48.10	0.00000		26.83	0.00000
Bone surfaces	4.07	0.87500		N/A	0.87500
Brain	14.06	2.88750		2.04	2.88750
Breasts	3.26	0.00175		0.93	0.00175
Colon	4.81	0.00001		N/A	0.00001
Eye Lenses	N/A	3.50000		N/A	3.50000
Gallbladder	4.81	0.00014		53.10	0.00014
Heart	24.79	0.00123		2.59	0.00123
Kidneys	6.29	0.00010		5.74	0.00010
Liver	7.77	0.00033		10.55	0.00033
Lower large intestine	5.18	N/A		7.77	N/A
Lungs	7.40	0.00534		2.96	0.00534
Muscles	3.70	0.06738		1.67	0.06738
Oesophagus	4.44	0.00306		N/A	0.00306
Osteogenic cells		N/A		2.04	N/A
Ovaries	5.18	0.00000		4.63	0.00000
Pancreas	4.81	0.00021		2.78	0.00021
Red marrow	4.07	0.18375		2.41	0.18375
Skin	2.89	0.21875		0.93	0.21875
Small intestine	4.44	0.00001		18.87	0.00001
Spleen	4.07	0.00038		2.78	0.00038
Stomach	4.07	0.00018		2.22	0.00018
Testes	4.07	0.00000		1.48	0.00000
Thymus	4.44	0.00306		1.11	0.00306
Thyroid	3.70	0.10500		1.11	0.10500
Upper large intestine	4.44	N/A		21.65	N/A
Uterus	6.66	0.00000		4.63	0.00000
Remaining organs	4.44	N/A		N/A	N/A
Effective dose(mSv)	7.03	0.12250		5.92	0.12250
					13.20

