8.4 Exclusion Criteria

- Patients with known allergic or hypersensitivity reactions to previously administered radiopharmaceuticals. Patients with significant drug or other allergies or autoimmune diseases may be enrolled at the Investigator's discretion.
- Adult patients who require monitored anesthesia for PET scanning.
- Patients who are too claustrophobic to undergo MRI or PET imaging.

- History of neurological disease known to affect cognition prior to initiating chemotherapy (e.g., stroke, head injury with loss of consciousness of >30 minutes, seizure disorder, demyelinating disorder, mental retardation, primary brain tumor, brain metastases, etc.)
- Current or past major psychiatric illness (e.g., schizophrenia, bipolar affective disorder)
- Evidence of stroke or mass lesion on CT or MRI scan
- History of alcoholism or other substance abuse
- Current use of cholinesterase inhibitors, other cognitive enhancers, antipsychotics, antidepressants, or anticonvulsant medications
- Current use of gabapentin or venlafaxine for hot flashes
- History of radiation therapy to the brain
- Uncontrolled diabetes or blood glucose >175 mg/dl on the day of the FDG-PET scan
- Currently pregnant
- Color blindness (cannot complete D-KEFS Stroop test)
- Moderate or Severe Depression as measured on the Beck Depression Inventory (BDI) – Short Form. The cut-off score for the BDI will be 8/9.

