8.5 Participant Registration

Participants must meet all of the eligibility requirements listed above and in Appendix A prior to registration.

Study related screening procedures can only begin once the participant has signed a consent form. Participants must not begin protocol procedures prior to registration.

To register eligible patients on study, a Clinical Trials Office Patient Registration Form will be completed and submitted to: [contact].

9 STUDY PROCEDURES, SCHEDULE of EVENTS, and TRACER ADMINISTRATION

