9.5 PET Exams

PET exams of [¹⁸F]Flutemetamol and [¹⁸F]FDG will be acquired in each participant. Two PET/CT scanning sessions will be required. This is due to fact that both [¹⁸F]Flutemetamol and FDG are labeled with F-18 that has a 110-minute half-life, which does not allow for same day imaging. The FDG and [¹⁸F]Flutemetamol study procedures will be obtained on separate days usually within 10-14 days of each other. Typically these will be obtained over two separate days (consecutive if possible). However, this may not be possible due to scheduling issues, weekends, and other variables. The days of imaging will be scheduled according to scanner and cyclotron availability, and all days of imaging will be obtained within six weeks of each other. The exact order and timing of the two PET imaging sessions will vary according to logistics, scheduling, and tracer availability. Patients who are not postmenopausal for a minimum of one year or surgically sterile must have a serum pregnancy test performed within 48 hours prior to each research PET imaging. The procedures for each PET scan are similar as described below.

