APPENDIX A: Eligibility Check List and Current Drug Use and Potential Toxicities

Patient Name: _____ Date: _____

MRN: _____ Person Confirming Eligibility _____

 (Yes/No) Patient is female. (Yes/No) Patient is \geq 18 years old. (Yes/No) Patient is \leq 70 years old. (Yes/No) Patient has a histologically proven diagnosis of Stage I through III C breast cancer (Yes/No) Patient has been previously treated with chemotherapy at least 6 months prior, but no more than 36 months prior to initial study scan.

Dates: _____

Type of Chemotherapy: _____

 (Yes/No) Patient must be postmenopausal for a minimum of one year, surgically sterile, or has been confirmed not to be pregnant by serum pregnancy test performed within 48 hours prior to research PET imaging.

If patient is postmenopausal, how far out are they from menopause: _____

If patient is of childbearing potential, date of negative pregnancy test: _____

 (Yes/No) Patient is not lactating. (Yes/No) Patient has no history of previous stroke, seizures, or other neurological disorders. (Yes/No) Patient agrees to have clinical and radiographic endpoints and results of histopathologic tissue analysis and other laboratory information entered into a research database, as evidenced by signing the informed consent form. (Yes/No) Patient does not have allergic or hypersensitivity reactions to previously administered radiopharmaceuticals. (Yes/No) Patient does not require monitored anesthesia for PET scanning or MRI imaging.

(Yes/No) Patient is not too claustrophobic to undergo MRI or PET imaging.

(Yes/No) Patients is able to lie still for 60 minutes.

(Yes/No) Patient does not have any MRI incompatible metal implants or clips.

(Yes/No) Patient has not been diagnosed with dementia or any other cognitive deteriorating conditions.

(Yes/No) Does patient have a family history of dementia? (Does not preclude participation in study)

(Yes/No) Is the patient right handed? (Informational for set up of fMRI study)

(Yes/No) Patient is not moderately or severely depressed as measured on the Beck Depression Inventory (BDI) –Short Form.

(Yes/No) Patient must report persistent cognitive problems following the initiation of chemotherapy, defined as being one or more standard deviations above normative data on our two scales of subjective cognitive dysfunction

- Cognitive Failure Questionnaire Score: _____ (Total score 45 or higher) _____
- Frontal System Behavioral Scale Score: _____ (T-score of 60 or higher) _____

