APPENDIX D: Schedule of Events

Test / Procedure	Screen	Research MRI study and Neuro-psychological Testing	PET Imaging Visit 1 First PET Exam Will depend on whether [¹⁸ F]-Flutemetamol or FDG study is performed	PET Imaging Visit 2 Second PET Exam Will depend on whether [¹⁸ F]-Flutemetamol or FDG study is performed
Inclusion / Exclusion Criteria	X			
Informed Consent	X			
Research MRI study		X		
Infusion of [¹⁸ F]Flutemetamol			X	X
[¹⁸ F]Flutemetamol PET Imaging			X	X
Adverse Event Questionnaire After [¹⁸ F]Flutemetamol study			X (3)*	X (3)*
¹⁸ F-FDG PET Imaging			X	X
Neuropsychological Testing		X		
Pregnancy Test (1)			X (2)	X (2)

* Performed immediately after [¹⁸F]Flutemetamol study

1 Patient must be postmenopausal for a minimum of one year, surgically sterile, or has been confirmed not to be pregnant by serum pregnancy test performed within 48 hours prior to research PET imaging.

2 GE requires all pregnancies that occur within 30 days of exposure to the investigational product be submitted to their institution. Patients will be contacted approximately 30 days post [¹⁸F]Flutemetamol scanning to collect information from the patient regarding pregnancy status.

3 A follow-up telephone call will be made to each participant within 1 day following their imaging scan with [¹⁸F]Flutemetamol. If the participant cannot be contacted at 1 day post-scanning, then we will continue trying to contact them for up to 7 days post-scanning.

4 The research MRI study and neuropsychological testing can be completed depending on staff availability and can be done before, after, or in between PET/CT imaging sessions.

Research MRI study

The research MRI study will include the following imaging sequences/studies. This is our current clinical brain tumor imaging protocol.

Scout

T1-weighted SE (pre injection)

T2

FLAIR;

Dynamic contrast enhanced images with associated T1 mapping

Diffusion- weighted imaging

Post T1-weighted SE

PET Imaging Visits 1 & 2:

Imaging of the PET tracers will be performed on two separate days with FDG imaging occurring on one day and [¹⁸F]Flutemetamol occurring on another day. The imaging will be performed on separate days depending on scheduling with the cyclotron. The days of imaging will be scheduled according to scanner and cyclotron availability, and all days of imaging will be obtained within six weeks of each other.

APPENDIX E: [¹⁸F]Flutemetamol Patient Adverse Event QuestionnaireCompleted at conclusion of [¹⁸F]Flutemetamol infusion.

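### Pregnancy must be ruled out before registration, but the only qualifying test is timed to PET and the MRI may come first, so the passages cannot all be followed

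*Combined protocol and SAP*

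**What the plan says.** On when pregnancy must be ruled out:

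- Section 8.4 lists "Currently pregnant" among the exclusions.
- Section 8.5 states "Participants must meet all of the eligibility requirements listed above and in Appendix A prior to registration" and "Participants must not begin protocol procedures prior to registration".
- Appendix A, the checklist that the investigator certifies, has a line that a woman meets by being at least a year past menopause, surgically sterile, or test-negative. The test is timed to the 48 hours before PET. A field below it reads "If patient is of childbearing potential, date of negative pregnancy test".
- Section 9.5 says that women who are neither a year past menopause nor surgically sterile "must have a serum pregnancy test performed within 48 hours prior to each research PET imaging".
- Appendix D marks the inclusion and exclusion criteria at Screen. It marks the pregnancy test under PET Visits 1 and 2 and nowhere else. Footnote 1 again requires a woman who is not postmenopausal or sterile to be "confirmed not to be pregnant by serum pregnancy test performed within 48 hours prior to research PET imaging". Footnote 4 lets the MRI and neuropsychological testing fall at any point relative to the PET sessions.

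On what the MRI contains, the Appendix D sequence list has a pre-injection T1, "Dynamic contrast enhanced images with associated T1 mapping" and a post T1. Section 9.4 describes task and resting-state fMRI with anatomical images, and section 10.3 an MPRAGE acquisition. Neither mentions an injection. The MRI risks in section 12.3 are metal, transdermal patches and claustrophobia.

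**The concern.** An exclusion criterion protects a participant only if it is checked before the procedures begin. Here the registration text says that it must be, while the schedule that staff would work from places the check at the PET visits and allows another study procedure ahead of it. Women are eligible from age 18, so some participants may be of childbearing potential; the protocol does not give their expected share.

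Two things are at stake. The first is that a woman whom the protocol means to exclude could have a study MRI before anyone has checked. The second is smaller: a pregnancy found at the first PET visit would turn an enrolled participant into a non-evaluable one. The plan allows 15 enrolled for 12 evaluable, so 15 − 12 = 3 spare places, and sections 1.2 and 10.5 justify these by blood-sampling failures, not by late ineligibility.

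**Working it through.** The plan states no figure to reproduce. The check is a cross-reading of the passages followed by date arithmetic.

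**Can all the passages be followed together?** Take a woman of childbearing potential whose MRI is her first study procedure.

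1. Section 8.5 puts registration before the MRI.
2. Section 8.5 with Appendix A puts the completed pregnancy line before registration.
3. Appendix A accepts, for her, only a serum test taken no more than 48 hours before PET.
4. The order is therefore test, registration, MRI, PET, with no more than 48 hours from test to PET.
5. Footnote 4 of Appendix D and section 8.1 set no such limit on the interval from MRI to PET.

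All the conditions hold only if registration, the MRI and the first PET scan fall inside one 48-hour test window. If the MRI is more than 48 hours before PET, a test taken before the MRI is too old to satisfy Appendix A, and a test that satisfies Appendix A comes after the MRI. Either the line cannot be completed and she cannot be registered, or Appendix D is followed and she is scanned with the criterion unverified.

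**How long can the gap be?** Put the MRI on day 0 and the two PET scans on separate days at the end of the window.

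| Limit | Source | Latest second PET | Latest first PET | First scheduled test | MRI ahead of test |
|---|---|---|---|---|---|
| Six weeks (6 × 7 = 42 days) | 9.5, Appendix D | day 42 | day 41 | days 39 to 41 | 39/7 = 5.6 to 41/7 = 5.9 weeks |
| Two months (59 to 62 days) | 8.1 | days 59 to 62 | days 58 to 61 | days 56 to 61 | 56/7 = 8.0 to 61/7 = 8.7 weeks |

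The lower figure in each row assumes that the test is taken as early as the 48 hours allow. Section 8.1 applies its limit to all three imaging sessions. Section 9.5 and Appendix D state theirs under the PET headings but refer to all days of imaging. Both rows are therefore shown.

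**Does another document step close the gap?** The MRI safety form in Appendix C asks about implants, metal, patches and similar items. It has no pregnancy question, so it does not supply the missing check.

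**Is contrast given?** The Appendix D list implies an injection between the pre- and post-T1 series. Sections 9.4, 10.3 and 12.3 describe none, and no agent is named anywhere. The documents do not settle the question.

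**The case against.** The best reply is that section 8.5 already prevents the problem. It bars protocol procedures before registration, and Appendix A asks for the date of a negative test on a form that the investigator certifies. Enforced literally, no woman of childbearing potential could reach the MRI untested. This stands as far as it goes, and it means that an untested MRI occurs only if the Appendix D grid is followed over section 8.5. It does not remove the conflict. The date field belongs to the line tied to PET, Appendix D schedules no screening test, and literal enforcement leaves an MRI-first participant unable to be registered unless everything fits within 48 hours.

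The second reply is that the test is aimed at radiation, and a serum test precedes each PET scan. That is correct, and nothing here suggests that PET is given without a test.

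Two stronger readings are tempting, and the documents do not support them:

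- A reader might infer that women will receive injected contrast before pregnancy is excluded. Contrast appears only in the Appendix D list, which is labelled as a clinical brain tumor protocol, omits the MPRAGE and functional sequences of the methods sections, and may have been carried over from elsewhere. The protocol also says nothing about MRI or contrast being hazardous in pregnancy.
- A reader might infer from footnote 2 of Appendix D that pregnancy follow-up is deficient after FDG, because the contact at about 30 days is timed from flutemetamol. That footnote carries out the manufacturer's reporting requirement for the investigational product and times it from flutemetamol. No passage requires the same follow-up after FDG, and a test precedes the FDG scan.

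**Conclusion.** The contradiction is real and narrow. Sections 8.4 and 8.5 and Appendix A place the exclusion of pregnancy before registration and before any procedure. Section 9.5 and Appendices A and D tie the only qualifying test to PET, and Appendix D permits the MRI first. For a woman of childbearing potential whose MRI is more than 48 hours before PET, the passages cannot all be met. If Appendix D governs in practice, the criterion can stay unverified after the MRI for about 5.5 weeks under the six-week limit, or about 8 weeks under the two-month limit. These are the permitted extremes, not expected intervals.

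The conclusion assumes that the MRI counts as a protocol procedure under section 8.5, and that Appendix D reads as the text shows, with no mark at Screen or the MRI visit. Its safety weight is undetermined until the documents agree on whether contrast is given. The number of women affected cannot be estimated from the documents. The primary binomial test and the sample-size calculation are not touched, and the possible loss of one of three spare places is conditional and small. It is worth correcting because it concerns a stated safety exclusion.

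**What to change.** Reconcile sections 8.4, 8.5 and 9.5 with Appendices A and D on when pregnancy status is confirmed relative to registration and to the first study procedure, so that the checklist line, the schedule table and footnote 4 can all be followed for every permitted order of visits. Separately, reconcile the MRI sequence list in Appendix D with sections 9.4, 10.3 and 12.3 on whether an injection is part of the study MRI. The sponsor and investigators choose the rule in both cases.

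The cost is wording in the schedule table, the checklist and a few sentences. Depending on the rule chosen, it may add at most one routine blood test for women of childbearing potential whose MRI comes first.

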9.4 Functional MRI Imaging

Functional Magnetic Resonance Images (fMRI) will be obtained using a Siemens 3.0 Tesla whole-body scanner equipped with a 32-channel multiband sed/receive head coil enabling rapid acquisition echo-planar imaging (EPI). Functional runs will consist of 405 frames per run [repetition time (TR) = 720 ms; echo time (TE) = 33.1 ms; flip angle = 52°, slice thickness = 2 mm; FOV = 208 mm; matrix = 104x90; voxel size = 2.0 mm³] of 72 transverse slices per volume. The first three EPI volumes acquired during each functional run will be excluded from further analysis in order to allow for steady-state transverse relaxation. Coplanar high-resolution anatomical images will be acquired using a isotropic gradient echo (MPRAGE) sequence [TR = 2.4s, TE = 2.14ms, TI = 1s, FA = 8, FOV = 224x224; vox size = 0.7 mm³] as well as an in-plane T2-weighted sequence [TR = 3.2 s; TE = 565 ms; FOV = 224x224 mm; slice thickness = 2 mm; matrix = 192 x 256] to allow precise localization of functional maps on brain anatomy.

Stimuli will be recorded and presented using ePrime running on a laptop personal computer. Functional image volumes will be acquired according to a boxcar-type stimulus paradigm

consisting of alternating (A-B-A-B) stimulus-ON and stimulus-OFF conditions. Each functional run will consist of repeated cycles divided into two alternating stimulus-ON and stimulus-OFF epochs. During stimulus-ON epochs, stimuli will be presented, whereas no stimuli (silence) will be presented during stimulus-OFF epochs. In addition, each functional run will be preceded by a short period of silence during which three pre-experimental baseline EPI volumes will be acquired. While in the MR scanner, subjects will be instructed to attend to the stimulus being presented, and to perform the task according to functional protocols.

Two functional runs will be collected according to the above protocol, using two independent task conditions designed to specifically probe higher cognitive functions implicated in chemobrain, namely working memory and relational processing.

Working memory task:

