The category-specific representations are used to probe working memory during this task condition. Participants will be presented with blocks of trials that consist of pictures of places, tools, faces and body parts (non-mutilated parts of bodies with no “nudity”). Within each run, the 4 different stimulus types will be presented in separate blocks. Within each run, 1/2 of the blocks use a 2-back working memory task and 1/2 use a 0-back working memory task (as a working memory load comparison). A 2.5 second cue indicates the task type (and target for 0-back) at the start of the block. Each of the two runs contains 8 task blocks (10 trials of 2.5 seconds each, for 25 seconds) and 4 fixation blocks (15 seconds). On each trial, the stimulus is presented for 2 seconds, followed by a 500 ms inter-task interval (ITI). Total scan time is 5:01.

Relational Processing task:

This task is adapted from Smith *et al.* 2007. Stimuli are 6 different shapes filled with 1 of 6 different textures. In the relational processing condition, participants are presented with 2 pairs of objects, with one pair at the top of the screen and the other pair at the bottom of the screen. They are told that they should first decide what dimension differs across the top pair of objects (differed in shape or differed in texture) and then they should decide whether the bottom pair of objects also differ along that same dimension (e.g., if the top pair differs in shape, does the bottom pair also differ in shape). In the control matching condition, participants are shown two objects at the top of the screen and one object at the bottom of the screen, and a word in the middle of the screen (either “shape” or “texture”). They are told to decide whether the bottom object matches either of the top two objects on that dimension (e.g., if the word is “shape”, is the bottom object the same shape as either of the top two objects. For both conditions, the subject responds yes or no using response buttons. For the relational condition, the stimuli are presented for 3500 ms, with a 500 ms ITI, and there are four trials per block. In the matching condition, stimuli are presented for 2800 ms, with a 400 ms ITI, and there are 5 trials per block. Each type of block (relational or matching) lasts a total of 18 seconds. There are 3 relational blocks, 3 matching blocks and 3 16-second fixation blocks. Total scan time is 2:56.

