Acquisition: 8 minutes of BOLD-EPI data will be collected with subjects lying in the scanner and instructed to simply 'lie still with your eyes open and think of nothing in particular'. We will concurrently monitor pulse oximetry and heart rate. These physiologic data serve two purposes: first, they serve as a 'real-time' proxy for assessment of subject discomfort and anxiety during the 8 minute data collection run, as subjects will be instructed to try not to talk during the run (unless in distress). Second, these data provide covariates for motion-related assessment and correction at data analysis stages. Additional motion-related signal change will be assessed by averaging time courses for two ROIs in white matter, CSF, soft tissues of the head, face, and scalp, and corrected within SPM using these and six rigid-body motion correction parameters from the 'Realign' step, following previously published procedures in our lab (Anderson et al., 2011b). After motion correction, resulting frames will be inspected for significant motion using the "scrubbing" procedure reported by Power et al. (2012), and frames with temporal derivative of root-mean-square variance over voxels (DVARS) or root-mean-square motion parameters >0.2 mm will be removed prior to analysis of connectivity results, with concatenation of remaining frames.

Analysis: 8-minute BOLD EPI scans will be coregistered with high-resolution anatomical volumes, normalized, and bandpass-filtered between 0.01 and 0.1 Hz. Signal fluctuation within 4 mm spherical seed regions of interest (ROI) representing major nodes within RSN hubs (representing sensorimotor, auditory, visual, speech, semantic, salience, executive function, and

default mode networks) will be cross-correlated with all other brain voxels. Correlation matrices will be constructed and significant pairwise correlation values will be represented in normalized brain space using subjects' anatomical MR image volumes. Groupwise network-level analyses will be carried out as above.

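### Appendix D specifies a contrast-enhanced brain tumor MRI list that no planned analysis uses, and it omits the MPRAGE and BOLD scans that 9.4 and 10.3 require

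*Combined protocol and SAP*

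**What the plan says.** Appendix D (Schedule of Events) introduces its MRI list with "The research MRI study will include the following imaging sequences/studies. This is our current clinical brain tumor imaging protocol". The seven entries are a scout, a T1 spin echo before injection, T2, FLAIR, "Dynamic contrast enhanced images with associated T1 mapping", diffusion, and a post T1 spin echo. The schedule puts the research MRI outside the Screen column, and footnote 4 says that it "can be done before, after, or in between PET/CT imaging sessions".

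Section 9.4 describes a different examination. It specifies an MPRAGE anatomical scan "as well as an in-plane T2-weighted sequence", and then task fMRI: "Two functional runs will be collected according to the above protocol, using two independent task conditions", one for working memory and one for relational processing. It adds a resting-state scan: "8 minutes of BOLD-EPI data will be collected with subjects lying in the scanner". Section 10.3 again specifies MPRAGE, for grey-matter volume and density compared with control cohorts scanned with the same sequence.

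Section 1.2 makes the anatomical and functional MRI information part of the study objective.

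**The concern.** The two descriptions of one scanning session barely overlap, and both are current text. Two things are at stake.

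The first is participant protection. A dynamic contrast series and a post T1 require an intravenous contrast agent. If the Appendix D list is followed, participants are injected with something that no analysis uses and that the supplied text does not otherwise mention.

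The second is the data. If site staff take Appendix D as the scan list, the MPRAGE and BOLD data behind the structural, task and resting-state analyses are never collected.

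**Working it through.** **Step 1. The plan's own design figure.** Section 10.5 gives n = 12, rejection at 4 or more positives, a null of 12%, an alternative of 42%, 80% power and one-sided 0.05. Exact binomial tails give P(X ≥ 4 | 12, 0.12) = 0.0464 and P(X ≥ 4 | 12, 0.42) = 0.8147. The figure reproduces. The outcome is flutemetamol positivity, with no MRI input, so this point does not touch the primary test.

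**Step 2. The two lists side by side.**

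| Acquisition | Required by | In Appendix D? |
|---|---|---|
| MPRAGE | 9.4, 10.3 | No |
| In-plane T2 | 9.4 | T2, by name only |
| Working-memory BOLD | 9.4 | No |
| Relational BOLD | 9.4 | No |
| Resting BOLD | 9.4 | No |

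The overlap is 1 of 5. Of the seven Appendix D entries, two need contrast (the dynamic series and the post T1) and one is their pre-injection baseline, so 3 of 7 are tied to an injection.

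**Step 3. Is contrast used anywhere?** Section 9.4 analyzes BOLD signal. Section 10.3 analyzes grey-matter volume and density. Section 10.4 names PET Z scores, SUVs and the composite SUVR as its imaging parameters. Section 10.1.2 co-registers FDG to the patient's MRI without asking for contrast. No section takes a dynamic-contrast, T1-map or post-contrast measure as input. FLAIR and diffusion also feed no analysis, but they need no injection.

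**Step 4. Is contrast covered by the safety text?**
- No agent or dose is named, and the Appendix D schedule has no renal check.
- Appendix C has 13 + 21 = 34 screening items over its two blocks. None asks about contrast reaction, kidney function or pregnancy.
- Section 12.3 describes MRI risks as metal, skin patches and claustrophobia. Its catheter risk is written for the radioisotope injection.
- The pregnancy test is set within 48 hours before each PET scan (9.5, Appendix D). Section 8.1 lets the three sessions spread over 2 months, so an MRI can fall outside that window.
- The adverse event questionnaire and the follow-up call are tied to the flutemetamol scan (Appendix D, Appendix E).

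**Step 5. BOLD time absent if Appendix D alone is used.** Section 9.4 gives 5:01 for working memory (301 s), 2:56 for relational processing ("Total scan time is 2:56", 176 s) and 8 minutes at rest (480 s).
- One working-memory run: 301 + 176 + 480 = 957 s, about 16 minutes.
- The working-memory text also says "Each of the two runs contains 8 task blocks". If that means two such runs: 2 × 301 + 176 + 480 = 1,258 s, about 21 minutes.

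**The case against.** The strongest reply is that the list is a leftover and no contrast is planned. The MRI is described elsewhere as anatomical and functional, 9.4 and 10.3 give full non-contrast parameters, 12.3 calls the MRI risk minimal, and Appendix C screens for nothing related to contrast. These silences fit an unused list as well as they fit missing safeguards. This stands. A reader might infer that participants will probably receive contrast because both lists will be run. The wording is not exclusive, so both could be run, but nothing shows that this is the likelier outcome.

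Three other strong readings also go too far.

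- *The contrast scan cannot serve the mass-lesion exclusion in 8.4, because 8.5 requires eligibility before registration.* Section 8.4 also excludes on blood glucose measured on the day of the FDG scan, so the plan does apply exclusions at imaging visits. A mass-lesion check is a possible use. The plan just does not assign it.
- *A woman could reach the MRI with no pregnancy check.* Appendix A includes the pregnancy item, and 8.5 requires Appendix A to be met before registration. What remains is that a test timed to PET need not be recent at the MRI. This matters only for women who are neither postmenopausal nor sterile, and their number is not given.
- *A contrast reaction would go unreported.* The 24-hour limit in 11.1 stands under expedited reporting, just after text that sends events unrelated to flutemetamol to the IRB by the routine route. Sections 11.2 to 11.4 add hospitalizations for grade 3 to 5 events, all deaths, and monitoring committee review of serious events.

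General protections also exist: the pregnancy exclusion and discretion over drug allergies (8.4), a lactation item (Appendix A), and MR staff screening under a neuroradiologist (12.3). None is specific to contrast. The consent pages were not available and could carry contrast wording. The institutional clinical MRI protocol was not supplied either and could hold the agent, dose and renal check. Neither would give the injection an analytic purpose in this plan or put MPRAGE and BOLD on the list.

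**Conclusion.** The point holds as a conflict in operative text that should be corrected. Appendix D lists 1 of the 5 required acquisitions and adds three injection-related entries that no analysis uses and no contrast-specific safeguard covers. Its consequence is conditional, because the documents do not settle which list would be run:

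- Appendix D run as written, alone or with the 9.4/10.3 scans: up to 15 participants (the enrollment ceiling in 1.2) receive an injection with no assigned purpose.
- Appendix D run alone: the exploratory MRI/fMRI analyses also lack their data, including 957 to 1,258 s of BOLD per participant.
- Appendix D list not run: neither harm occurs, and the error is confined to the document.

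The primary amyloid test is unaffected in every case. The statement on safeguards rests on the supplied text, without the consent pages or the institutional MRI protocol.

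**What to change.** Replace the Appendix D list with what 9.4 and 10.3 require: scout, MPRAGE, in-plane T2, the task-BOLD runs and resting BOLD. Delete the pre-injection T1, the dynamic contrast series and the post T1. Keep FLAIR and diffusion only with a stated purpose, such as the stroke or mass-lesion check in 8.4.

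Only if contrast is truly intended, state its purpose, name the agent and dose, require renal, allergy and pregnancy screening before the MRI, add risk text to 12.3, and provide for adverse event capture after the MRI.

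The main change is one appendix amendment. It adds no visits, and removing the contrast entries shortens the MRI if they would otherwise be run. Keeping contrast costs more: 8.4, 11.1, 12.3, Appendices A and C and the pregnancy-test row would also need changes.

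As separate housekeeping while 9.4 and 10.3 are open, settle the MPRAGE resolution (0.7 mm in 9.4, 1.0 mm in 10.3), the number of working-memory runs, and the frame and volume counts (405 and 192) in 9.4.
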